7.2.2 Secondary endpoints

The following 4 secondary endpoints are defined for the study.

R-wave amplitude

The **secondary endpoint 1** evaluates the R-wave amplitude at the 1st follow-up and at 3-month follow-up by measuring both, the lowest and the highest amplitude value via the programmer.

Noise burden

The **secondary endpoint 2** evaluates the noise burden at the 1st follow-up and at 3-month follow-up by retrieving the percentage of noise via the programmer.

Assessment of P-wave visibility

The **secondary endpoint 3** evaluates the P-wave visibility at 1st, 3- and 12-month follow-up. The investigator will evaluate whether P-waves can be recognized in the stored sECGs showing sinus rhythm. The number of heart cycles and observed P-waves which can undoubtedly be identified in ECGs will be assessed by the investigator.

SADE-free rate until the 12-month follow-up

The **secondary endpoint 4** is the SADE-free rate related to the BIOMONITOR III 12 months after insertion.

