2 SYNOPSIS

Title	BIO MASTER.BIOMONITOR III
Patient population	The patient population consists of patients in whom long-term cardiac rhythm monitoring is required for diagnostic purposes.
Design	Multicenter, international, prospective, non-randomized, non-controlled, open-label
Investigational device(s)	BIOMONITOR III insertable cardiac monitor, including incision and insertion tool (FIT OneStep)
Objectives	This study is a post-market clinical follow-up (PMCF) study to identify and evaluate residual risks associated with the use of the BIOMONITOR III that are discovered or remain even after risk analysis, risk mitigation and successful conformity assessment. Furthermore, this study will also provide additional data as required by regulatory authorities outside of the CE-region.
Primary endpoint	SADE-free rate related to BIOMONITOR III including incision and insertion tool set until 3-month follow-up
Secondary endpoint(s)	
 • R-wave amplitude at 1st follow-up and 3-month follow-up • Noise burden at 1st follow-up and 3-month follow-up • P-wave visibility at 1st follow-up and 3-month and 12-month follow-up • SADE-free rate related to BIOMONITOR III from insertion until 12-month follow-up
Inclusion criteria	
 • Patient is at high risk of developing a clinically important cardiac arrhythmia; or Patient is undergoing investigation for symptoms such as palpitations, pre-syncope or syncope, that are suggestive of an underlying cardiac arrhythmia; or Patient is undergoing investigation for the detection of atrial fibrillation following cryptogenic stroke; or Patient is planned for AF ablative procedure or

has already undergone an AF ablative procedure.

- Patient is able to understand the nature of the study and able to provide written informed consent.
- Patient is willing and able to perform all follow-up visits at the investigational site.
- Patient is willing and able to use the CardioMessenger and accepts the BIOTRONIK Home Monitoring concept.

Exclusion criteria

- Patient is implanted with an ICD or pacemaker.
- Patient is pregnant or breast-feeding.
- Patient is less than 18 years old.
- Patient's life-expectancy is less than 12 months.
- Patient is participating in another interventional clinical investigation.

Study duration Sep 2019 – Aug 2021

Sample size 157

Investigational sites Up to 30

Number of follow-ups per patient 4 (including insertion)

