5.2.1 BioMonitor Master Study¹

The objective of the BioMonitor Master study (NCT01725568) was to confirm the safety and efficacy of BioMonitor (first generation ICM) and to collect PMCF data. 152 patients were inserted in 17 clinical sites in 6 countries. The first patient was recruited on October 31, 2012, last patient out was on October 10, 2014. The observation time was one year. No device related and 4 procedure related serious adverse device effects (SADE) occurred. Regarding the efficacy of the BioMonitor, 77 assessments of the QRS-detection performance of the BioMonitor were performed. In 72 cases, the QRS-detection was appropriate which yields in a rate of 93.5%. Only 5 patients provided a QRS-detection positive predicted value (PPV) lower than 90% (Min 85.5%). The mean value of the R-wave amplitude was 0.3 mV over the study observation time. The overall performance of the implantable cardiac monitor BioMonitor was within the expected range. Therefore, BioMonitor was evaluated as safe and efficacious.

¹Clinical Investigation Report of the BIO|Master.BioMonitor study of the Implantable Cardiac Monitor BioMonitor, Version 1.0. 2015

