7.2 Endpoints and hypotheses

7.2.1 Primary endpoint and hypothesis

SADE-free rate until the 3-month follow-up

A primary endpoint is an SADE (see definition in section 18) that is possibly, probably or causally related to the BIOMONITOR III, the Incision Tool or the Insertion Tool, or the insertion procedure, which occurs before the 3-month follow-up.

SADEs will be adjudicated by an internal adjudication board, whereby the seriousness and device relatedness will be re-examined. If any amply documented external physical influence (e.g. accident, sport) or medical AE caused the SADE, it does not contribute to this endpoint. SADEs that occur later than the 3-month follow-up, and SADEs with onset date later than 105 days after insertion procedure (3 months defined as 91 days after implantation + 14 days would still be in accordance to the CIP) in case the 3-month follow-up was not conducted or conducted outside the specified time interval, do not contribute to this endpoint.

The parameter of interest p_{SADE} is the SADE free rate, which will be calculated by

$$1 - \frac{\text{Number of patients with one or more primary endpoint until the 3 months FU}}{\text{Number of patients at the 3 months FU or with primary endpoint}}$$

in percent. The period of observation starts with the insertion of the BIOMONITOR III and takes until the 3-month follow-up.

It is expected, that the SADE-free rate will be significantly above 90%. Therefore the corresponding hypotheses definitions are:

Null hypothesis:

$$H_0 : p_{SADE} \leq 90\%$$

Alternative hypothesis:

$$H_A : p_{SADE} > 90\%$$

The following patients are not included in the analysis set for this endpoint:

- Patients without SADE, prematurely terminated before the time window for the 3-month follow-up, i.e. less than 77 days after insertion procedure (3 months defined as 91 days after implantation – 14 days would still be in accordance to the CIP).

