8.1.3 Selection of measurements for endpoints

For the primary endpoint, the SADE-free rate will be assessed by collecting and evaluating adverse events until the 3-month follow-up (see section 7.2.1).

For **secondary endpoint 1**, the R-wave is measured via the programmer. Due to its automatic measurement, this figure unambiguously indicates the device's ability to detect the patient's heart beats. The noise burden for **secondary endpoint 2** is continuously recorded by the device. The value retrieved from the device with the help of the programmer clearly measures the time during which the device is unable to detect the patient's heartbeats.

P-waves are not detected by the device; therefore, the investigators decide whether P-waves are visible in a test ECG. A periodic sECG was chosen as the sample ECG because during arrhythmia, P-waves are often not present. The P-wave visibility (**secondary endpoint 3**) is determined by counting P-waves and QRS-complexes.

For the **secondary endpoint 4** the long-term safety of the BIOMONITOR III system, all SADEs related to the BIOMONITOR III system are collected by the investigators and evaluated by an internal adjudication board as described above. An observation period of 12 months was chosen to significantly extent the monitoring period for safety events beyond the 3 months which are defined for the primary endpoint.

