18.2.1 Causality Assessment

The relationship between the use of the investigational device (including the medical-surgical procedure) and the occurrence of each adverse event shall be assessed and categorized, considering the presence of confounding factors, such as concomitant medication and treatment, the natural history of the underlying disease, other concurrent illness or risk factors.

Each AE will be classified according to five different levels of causality. As defined in the Meddev 2.7/3 rev 3, the investigator will use the following definitions to assess the relationship of the serious adverse event to the investigational device or procedures and the sponsor will review the investigator's categorization:

Not related: the relationship to the device or procedures can be excluded.

Unlikely: the relationship with the use of the device seems not relevant and/or the event can be reasonably explained by another cause, but additional information may be obtained.

Possible: the relationship with the use of the investigational device is weak but cannot be ruled out completely. Alternative causes are also possible (e.g. an underlying or concurrent

illness/clinical condition or/and an effect of another device, drug or treatment). Cases were relatedness cannot be assessed or no information has been obtained should also be classified as possible.

Probable: the relationship with the use of the investigational device seems relevant and/or the event cannot be reasonably explained by another cause, but additional information may be obtained.

Causal relationship: the serious event is associated with the investigational device or with device procedures without reasonable doubt.

The investigators will distinguish between adverse events related to the investigational device and those related to the device procedures (any procedure specific to the investigational device). Procedure related events refer to the procedure related to the application of the investigational device only and therefore not to any other procedure for other devices and not to any other procedures or treatments applied later throughout the clinical investigation, for instance to treat (serious) adverse events. In case of a replacement of the investigational device in response to an adverse event (e.g. lead replacement after dislocation), the replacement will be considered like an initial application of a new investigational device and shall be assessed accordingly.

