### 14.1. Analysis set

All analyses are performed for the full analysis set.

For the calculation of the Kaplan-Meier analysis, the following time variables will be used:

1. For patients with at least one primary endpoint: time from insertion to time of first primary endpoint (sar\_aestdt\_first).
2. For patients without primary endpoint: time from insertion to last information available (sar\_time\_max).

For the KM analysis data of all patients is used.

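### The CIP and SAP disagree on which SADEs count in the 12-month SADE-free rate (secondary endpoint 4), and the event flag in SAP 14 does not settle it

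*Protocol*

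**What the plan says.** **Primary endpoint (3 months).** CIP 7.2.1 counts SADEs that are "possibly, probably or causally related to the BIOMONITOR III, the Incision Tool or the Insertion Tool, or the insertion procedure". The synopsis shortens this to "SADE-free rate related to BIOMONITOR III including incision and insertion tool set until 3-month follow-up".

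**Secondary endpoint 4 (12 months).** There are three descriptions:

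- *Short label.* CIP 7.2.2 says that the endpoint "is the SADE-free rate related to the BIOMONITOR III 12 months after insertion". The synopsis has "SADE-free rate related to BIOMONITOR III from insertion until 12-month follow-up", with no mention of the tool set. CIP 5.3 repeats the short label, but gives the purpose as confirming the safety of the system from insertion to 12 months.
- *System.* CIP 8.1.3 says that "all SADEs related to the BIOMONITOR III system are collected by the investigators and evaluated by an internal adjudication board as described above". CIP 7.1 speaks of the system as including the insertion procedure, and 7.1.1 assesses system safety through SADEs related to the device, both tools and the procedure.
- *Primary-endpoint flag.* SAP 14 opens with the 7.2.2 text. SAP 14.1 then sets the event time as follows: "For patients with at least one primary endpoint: time from insertion to time of first primary endpoint". SAP 14.2 lists AERELPET as the only event variable. SAP 10.1 sets AERELPET to Yes only when every condition of CIP 7.2.1 is met, and one of those conditions is the 3-month time limit.

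**Coding at sites.** CIP 18.2.1 states: "The investigators will distinguish between adverse events related to the investigational device and those related to the device procedures".

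**The concern.** Device and procedure relatedness are recorded separately, so the wording of the endpoint can decide whether an event counts. If the 12-month rate were restricted to device-related SADEs, a serious event coded as procedure-related only would count at 3 months and be absent at 12 months. The long-term figure could then look better than the short-term one, and the two could not be compared.

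This matters in this study because CIP 5.3 gives the smaller device and the new incision and insertion tools as the reason for a safety primary endpoint. Procedure-related events can also dominate: for the first-generation device, CIP 5.2.1 reports "No device related and 4 procedure related serious adverse device effects (SADE) occurred".

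**Working it through.** **1. The plan's own figures.** No rate, threshold or sample size is stated for secondary endpoint 4. The figures in CIP 11.2 belong to the primary endpoint and can be reproduced.

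- Normal approximation: n = [(1.960·√(0.90·0.10) + 1.282·√(0.97·0.03)) / 0.07]² = 132.8, so 133. With 10% drop-out, 133/0.9 gives 148.
- Exact binomial at n = 141: success needs at least 134 SADE-free patients (at most 7 with events), with one-sided alpha 0.0242 and power 0.937. Power is below 90% for n = 131 to 140 and above it for every n from 141 to 160, the end of the range checked. 141/0.9 gives 157.

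None of this depends on secondary endpoint 4.

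**2. Relatedness and time window, side by side.**

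| Source | Relatedness | Window |
|---|---|---|
| CIP 7.2.1 (primary) | device, both tools, procedure | to the 3-month visit; day 105 if that visit is missed or out of window |
| CIP 7.2.2, 5.3, synopsis (SE4) | BIOMONITOR III | 12 months |
| CIP 8.1.3 (SE4) | BIOMONITOR III system | 12 months |
| SAP 14, through AERELPET (SE4) | device, both tools, procedure | limit inherited from 7.2.1 |

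The SAP row has the wide relatedness scope but the wrong window. An SADE after the 3-month window fails a 7.2.1 condition and is not flagged. Apart from events between day 90 and the close of that window, the 365-day Kaplan-Meier estimate in SAP 14.5 therefore repeats the 90-day estimate in SAP 10.3. A working 12-month analysis needs a new flag, and the CIP gives two wordings from which to build it.

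**3. Effect of the literal device-only reading.** Take n patients, all followed up. Let d be those with a device-related SADE by 3 months, k those with only tool- or procedure-related SADEs by 3 months, and m those with a first device-related SADE after 3 months.

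- 3-month rate, 7.2.1 scope: 1 − (d + k)/n
- 12-month rate, device only: 1 − (d + m)/n
- Difference (12-month minus 3-month): (k − m)/n, which is positive whenever k > m

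**4. Size, from the documents.** In the first-generation study (CIP 5.2.1: 152 patients, one year, 0 device-related and 4 procedure-related SADEs):

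- Device only: 152/152 = 100%
- 7.2.1 scope: 148/152 = 97.4%, if the four SADEs were in four patients (exact 95% CI for the event rate 0.7% to 6.6%)

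**5. Size, with assumed events.** Take n = 141 with complete follow-up, four patients with early procedure-only SADEs, and one other patient with a late device-related SADE.

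| Rate | SADE-free | Exact 95% CI |
|---|---|---|
| 3 months, 7.2.1 scope | 137/141 = 97.2% | 92.9 to 99.2 |
| 12 months, device only | 140/141 = 99.3% | 96.1 to 100.0 |
| 12 months, AERELPET as in SAP 14 | 137/141 = 97.2% (late event not flagged) | 92.9 to 99.2 |
| 12 months, one aligned definition | 136/141 = 96.5% | 91.9 to 98.8 |

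**6. Estimator.** The 3-month rate is a crude proportion that leaves out event-free patients terminated before day 77 (SAP 10.1). The 12-month rate is Kaplan-Meier on all patients (SAP 14.1). Assume 157 patients, four early events and 16 event-free early terminations, all after those events. The crude rate is 137/(157 − 16) = 137/141 = 97.2%, and the Kaplan-Meier rate is 153/157 = 97.5%. Even with identical scope, the 12-month figure can be the higher one.

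**The case against.** The strongest reply is that the short label is only shorthand. The synopsis line for the primary endpoint and CIP 11.6 both leave out the insertion procedure. Read strictly, they would contradict 7.2.1, so these one-line labels are not complete scopes. CIP 4.3 names the investigational device as including both tools. CIP 18.2 counts harm from insertion as an adverse device effect, 18.2.1 treats use of the device as including the surgical procedure and lets an event be related to both, and 18.7 classes insertion-site infection and dehiscence as adverse device effects. CIP 8.1.3 presents the 12-month endpoint as a longer observation period, not a narrower kind of event. Secondary endpoint 4 is also hypothesis-free (SAP 5.2), exploratory (SAP 5.3) and outside the pass/fail rule (CIP 11.5).

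Most of this stands. It makes the wide scope the more likely intention and limits the consequence. A reader might infer that the planned analysis will report a 12-month rate above the 3-month rate because tool and procedure events are dropped. The documents do not support that: SAP 14 has no device-only filter. Nor would a higher 12-month figure prove a scope mismatch, because the two estimators differ.

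The reply does not remove the conflict. CIP 7.2.2 is the defining text, and it uses neither the term system nor the 7.2.1 list. SAP 14 quotes that text and analyses something else. Its flag must be replaced because of the time limit, and whoever writes the replacement from 7.2.2 alone could adopt the device-only reading.

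**Conclusion.** The relatedness scope of secondary endpoint 4 is inconsistent between CIP sections and between the CIP and the SAP, and should be corrected. The SAP does not cure this, because AERELPET joins the wide scope to a 3-month limit.

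Only under a literal device-only reading, which SAP 14 does not implement, would procedure-only SADEs counted at 3 months drop out at 12 months. The size of that effect is illustrated by 100% against 97.4% in the first-generation study. That figure assumes four different patients and comes from an earlier device with other insertion tools. It compares two scopes over one year, not two time points, because event timing is not given. The counts in the n = 141 and n = 157 examples are assumptions.

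The primary endpoint, its test and the sample size are not affected.

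**What to change.** - In the synopsis, CIP 5.3, 7.2.2 and 8.1.3, and SAP 14, define secondary endpoint 4 with the 7.2.1 relatedness scope: device, incision tool, insertion tool or insertion procedure, rated possible, probable or causal. The period runs from insertion to the 12-month follow-up.
- In SAP 14, replace AERELPET with a 12-month event flag of that scope and no 3-month cut-off. Take the event time from the first event so flagged; the variable now named, sar_aestdt_first, is labelled in SAP 8 as the onset of the first AE.
- If a device-only rate is wanted, report it as a separate, labelled line.
- Compare 12 months with 3 months on the same Kaplan-Meier estimator. SAP 10.3 already provides the 90-day value.

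**Cost.** A sentence in each place and one new evaluation variable. No new patient data are needed: relatedness is already recorded under CIP 18.2.1, and 8.1.3 already sends these SADEs to the adjudication board. The reported 12-month rate may be slightly lower. The primary test and N = 157 do not change.

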7.3 Claims and intended performance

Recent changes in legislature require that any statements made for the promotion of medical products must be based on scientific evidence. These statements are called 'promotional claims'.

In this clinical investigation the following promotional claims shall be supported:

Table 2: List of promotional claims related device features and study endpoint.

Promotional Claim	Feature	Related endpoints / data of interest
[REDACTED]	[REDACTED]	[REDACTED]
[REDACTED]	[REDACTED]	[REDACTED]

Promotional Claim	Feature	Related endpoints / data of interest

-
 
[REDACTED]
 
[REDACTED]
 
[REDACTED]
 
[REDACTED]
	
[REDACTED]
 
[REDACTED]
	
[REDACTED]

[REDACTED]
 
[REDACTED]
	
[REDACTED]
 
[REDACTED]
	
[REDACTED]

[REDACTED]
	
[REDACTED]
	
[REDACTED]

7.4 Safety assessments

The primary endpoint addresses the safety of the study device. Further, all adverse events will be recorded and summarized (see section 18). These events will be assessed as defined in the SOPs of the sponsor.

7.5 Further data of interest

Beyond the objectives defined in section 7.1, the study is designed to collect further data of interest. The data on the following topics will be considered 'data of interest' and may be analyzed, as appropriate:

- Demographics
- Medical history
- Indication for ICM
- Usage of incision tool and assessment of incision tool handling
- Assessment of insertion procedure: performance of insertion tool and ease of use (e.g. insertion time, handling and positioning)
- Insertion site
- Insertion success rate
- Wound closure
- Positioning of BIOMONITOR III
- Comfort after wound healing
- Explantation data of BIOMONITOR III
- Additional implantation of BIOMONITOR III
- Serial number of used study devices

- Performance of arrhythmia detection (will be assessed by comparing the BIOMONITOR III detected arrhythmia episodes recorded against a 48-hour Holter ECG, if applicable)
- Syncope and AF: detailed analysis of sensing performance in device-triggered ECG- episodes
- AF burden
- Assessment of device programming: individualized programming and re-programming of the device
- Assessment of programmer and programmer software performance
- Remote Assistant III trigger success rate after insertion procedure
- Home Monitoring Data (e.g. transmission success)
- HM workflow efficiency
- Assessment of BIOMONITOR III repositioning (if applicable)
- Assessment of BIOMONITOR III migration (if applicable)
- Usability of Patient App (if applicable)
- Information on application of imaging techniques, if applicable (e.g. MRI, mammography)
- Diagnosis and further treatment
- Adverse events and device deficiencies

8 DESIGN OF THE CLINICAL INVESTIGATION

8.1 General considerations

8.1.1 Type of clinical investigation

The BIO|MASTER.BIOMONITOR III is designed as an open, prospective, single arm, non-randomized international study.

8.1.2 Measures taken to minimize or avoid bias

No randomization or blinding of the investigator is necessary in this study, because the study does not require a control group. The clinical investigation is designed and will be conducted, analyzed, and reported based on an internal Standard Operating Procedure (SOP) system to minimize and avoid any bias.

It is planned to conduct this study in approximately 30 international sites with several physicians per site. Thereby an adequate level of heterogeneity of countries, sites and investigators is ensured to obtain representative results.

To minimize bias from very high recruitment rates of single sites, a limitation of the maximum number of patients per site is defined for the study. To minimize site-specific bias, the maximum number of patients per center will be n=30.

